2. DEFINITIONS

2.1 Active cancer

Cancer diagnosed within the previous six months; recurrent, regionally advanced or metastatic cancer; cancer for which treatment has been administered within the past six months; or haematological cancer that is not in complete remission. Basal cell or squamous cell carcinoma of the skin are excluded from this definition.

2.2 End-of-life care

A patient is considered in end-of-life care in case of a confirmatory negative response of the healthcare professional to the question “Would you be surprised if this patient died in the next 6-12 months?”, which is an accurate and widely used trigger for referring a patient to specialist palliative care.^{1,2}

3. BACKGROUND

Deprescribing (i.e., discontinuing medication) is an important part of palliative care to prevent polypharmacy, which is associated with increased risk of adverse drug events, drug-drug and drug-disease interactions, reduced functional capacity, multiple geriatric syndromes, medication nonadherence, and higher healthcare costs. One of the most widely used cardiovascular drug classes in cancer patients in a palliative setting are antithrombotics, including anticoagulant and anti-platelet agents. Antithrombotic drugs, e.g., (DOACs), low-molecular-weight heparins (LMWH), vitamin-K antagonists (VKA) and so-called antiplatelet agents (such as acetyl salicylic acid and P2Y12 inhibitors), are indicated in patients with prosthetic heart valves, in those with venous thromboembolism (VTE), for stroke prevention in atrial fibrillation as well as in patients with established atherosclerotic cardiovascular disease (such as myocardial infarction, stroke, or peripheral artery disease). Most patients have been receiving these drugs chronically before their cancer was diagnosed, whilst others are being prescribed them in order to treat or prevent cancer-associated thrombosis. Obviously, decisions on deprescribing antithrombotics heavily depend on the indication of the antithrombotic drug in addition to patient and healthcare professional preferences and experience, and on the estimated life expectancy of the patient.

Understanding current patterns of management of antithrombotic therapy (ATT) as well as the rationale and preferences behind these patterns is crucial for improving clinical practice. Since deprescribing patterns and rationale may largely differ across countries, relevant data at a large scale is needed to fully understand and appreciate the relevant decision processes.

The insights gained in this study are a first step towards the development of a clinical decision tool supporting decisions on ATT in cancer patients.

4. STUDY OBJECTIVE(S)

- >To explore and describe current European practice patterns with regard to the use of ATT in end-of-life care of cancer patients following 'flash mob research (FMR)' methodology.
- To evaluate and understand the processes and factors that inform decisions concerning the deprescription of ATT in the last year of life of cancer patients receiving ATT via a discrete choice experiment (DCE) among healthcare professionals, who deal with end-of-life care in cancer patients, or prescribe such medication to cancer patients.

5. STUDY DESIGN

International cross-sectional qualitative (flash mob research) study conducted as survey among healthcare professionals across Europe.

6. STUDY POPULATION

SERENITY aims to enrol healthcare professionals from various institutions across Europe, who deal with end-of-life care in cancer patients, or prescribe ATT to cancer patients.

These will involve general practitioners, palliative care specialists, nursing home physicians, geriatricians, vascular medicine specialists, oncologists, haematologists, pulmonologists, cardiologists, neurologists, and vascular surgeons with equal gender representation and distribution of experienced versus less experienced (young professionals) physicians.

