10. DESCRIPTION OF STUDY PROCEDURES

The study will be divided into three phases: the recruitment phase, the FMR-phase and the data analysis phase.

In the **recruitment phase**, the national coordinators of the project group will advertise the study through traditional professional networks as well as their social media channels. Information about the study will be distributed via personal communication, relevant scientific organisations and journals, and via social media. The healthcare professionals of interest will be invited to pre-register for study participation so they can be assigned a unique link to the electronic case report forms (eCRF). During the preregistration, characteristics of the pre-registrants will be checked (i.e., sex, age, profession, years of experience, the country where they are practicing, and the number of cancer patients in palliative care whom they care for on a yearly basis).

In the **FMR phase**, all preregistered participants will be asked simultaneously to complete the survey using the *Castor electronic data capture platform* within seven days.

The survey will be divided into the following sections:

- a) **General questions** regarding end-of-life care (e.g., "When do you consider a patient in end-of-life care?") and (de)prescription of antithrombotic medication to cancer patients during end-of-life care (e.g., "Have you ever considered deprescribing antithrombotic medicine?").
- b) A sequence of **choice scenarios** i.e., hypothetical scenarios that vary with regard to several characteristics (**attributes**; e.g., bleeding risk, thrombotic risk). Attributes will be further specified by varying choice levels (**attribute levels**; e.g., low or high bleeding risk), which are considered relevant for the decision on continuation or stopping antithrombotic medication in the patient population studied. In accordance with the discrete choice experiment (DCE) methodology, participants will be asked to select the healthcare intervention (i.e., either continuation or discontinuation of the antithrombotic therapy) that in their opinion would benefit the patient the most within each choice set.
- c) Participants will be asked to share **actual case decisions** they made in a maximum of three consecutive cases involving patients with active cancer, who were considered to receive end-of-life care. Fully anonymised data of the patients (sex, age category, primary tumour, tumour

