15. APPENDICES

15.1 Survey: Questions for pre-registration

1. Please select your country (*Denmark; France; Germany; Italy; The Netherlands; Poland; Spain; United Kingdom*)
2. Please select your age category (*25-34; 35-44; 45-54; 55-64; 65 or older*)
3. Please select your sex (*male; female; other*)
4. Please select your profession (*general practitioner; palliative care specialist; nursing home physician; geriatrist; vascular medicine specialist; oncologist; haematologist; pulmonologist; cardiologist; neurologists; vascular surgeon*)
5. Please select the professional experience group that matches your years of experience (*< 5 years; 5-10 years; 11-15 years; 16-20 years; 21 or more*)
6. Please provide an estimate on the number of patients you see/treat with active cancer each year, who are considered to be in end-of-life care.
This number is important for the upcoming data collection.

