15.2 Survey: General questions

1. When do you consider a patient in end-of-life care? If the life expectancy is:
A. < 1 year B. < 6 months C. < 3 months D. < 2 weeks
2. When a patient is considered to be in end-of-life care, I **XXX** prescribe antithrombotic medication upon the diagnosis of a thrombotic complication.
A. never B. sometimes C. often D. always
3. Have you ever deprescribed (i.e., terminated) antithrombotic medication in end-of-life care of cancer patients?
A. no B yes

In case of no, the participant will not be redirected to certain questions.

4. When a patient is considered to be in end-of-life care, I **XXX** deprescribe antithrombotic medication.
A. never B. sometimes C. often D. always
5. Give an estimate of the frequency per year that you consider deprescribing antithrombotic medication in patients, considered to be in end-of-life care:
XXX /year
6. Give an estimate of the frequency per year that you actually deprescribed antithrombotic medication in patients considered to be in end-of-life care:

XXX /year

7. Do you discuss deprescription of antithrombotic medication in patients at the end of life with colleagues?
A. never B. sometimes C. frequently D. always
8. Please indicate what factors determine whether you prescribe antithrombotic medication in patients considered to be in end-of-life care.
9. Please indicate what factors determine whether you deprescribe antithrombotic medication in patients considered to be in end-of-life care.

15.2.1 Examples of factors relevant to questions 8 and 9

1. Antithrombotic medication:
 - DOAC or VKA
 - LMWH (therapeutic)
 - Antiplatelet agent
2. Indication for antithrombotic medication:
 - Atrial fibrillation
 - Treatment of acute VTE event or prevention of (recurrent) VTE
 - Mechanical heart valves
 - Other indication
3. Bleeding risk:
 - Low
 - High
4. Thrombotic risk:
 - Low
 - High
5. Sex:
 - Female
 - Male
 - Other
6. Age:
 - < 40 years
 - 40-75 years
 - > 75 years
7. Patient's performance status:
 - Eastern Clinical Oncology Group performance status (ECOG-PS) grade 0-2
[Oken MM et al. Am J Clin Oncol. 1982]
 - ECOG-PS grade ≥ 3
8. Patient prognosis:
 - < 6 months
 - < 3 months
 - < 2 weeks

9. Patient preference:

- Stop antithrombotic treatment
- Continue antithrombotic treatment

10. Other

Free text

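### Section 15.2 question 2 can record a lack of end-of-life cancer patients as *never* prescribing, and section 13 sets no denominator to separate the two

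*Combined protocol and SAP*

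**What the plan says.** Section 6 defines the population by two alternatives: professionals "who deal with end-of-life care in cancer patients, or prescribe ATT to cancer patients". Either one suffices.

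Section 10 says that "The healthcare professionals of interest will be invited to pre-register for study participation" and that "During the preregistration, characteristics of the pre-registrants will be checked". The characteristics listed include profession and "the number of cancer patients in palliative care whom they care for on a yearly basis". ATT prescribing is not among them. No threshold or consequence is given for any answer, and the section goes on: "all preregistered participants will be asked simultaneously to complete the survey".

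Section 15.1 has six items: country, age, sex, profession, experience, and question 6, "Please provide an estimate on the number of patients you see/treat with active cancer each year, who are considered to be in end-of-life care". The answer is an open estimate, so zero is possible.

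In section 15.2, question 2 (prescribing after a thrombotic complication) and question 4 (deprescribing) both concern patients in end-of-life care. Both use the scale "A. never B. sometimes C. often D. always". Between them, question 3 asks whether the respondent has ever deprescribed in this setting. A note says that those answering *no* are not taken to certain questions, without naming them.

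Section 13 plans a descriptive main analysis with 95% confidence intervals, overall and by subgroup. It states no denominator for these items.

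**The concern.** The population admitted by section 6 is wider than the population that the practice questions describe. Objective 1 concerns ATT use in end-of-life care of cancer patients. A clinician who prescribes ATT to cancer patients but has none at the end of life is eligible, receives the survey, and is asked how often he or she prescribes in a setting never met in practice. The scale gives this person no accurate answer other than *never* or a blank.

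Two different facts then share one category: a clinician who sees these patients and chooses not to prescribe, and a clinician who sees none. Only the first is a practice pattern. The mixing raises the reported *never* share. If the unexposed share differs between professions or countries, part of any difference between them would reflect who has such patients. A larger sample does not help, because it narrows the interval around a shifted percentage.

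**Working it through.** The plan gives no figure for this point. The check is therefore a tracing of the text, followed by an illustration on assumed inputs.

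**Tracing a registrant who enters 0 at question 6 of section 15.1**

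1. *Section 6.* Zero means that the first alternative is not shown. The second may still hold, so the person may be fully eligible. No item on ATT prescribing settles it.
2. *Section 10.* The number is checked, but nothing follows from a zero. The survey goes to all preregistrants.
3. *Section 15.2, question 2.* No filter precedes it. The possible responses are *never* or a blank, unless the person answers hypothetically.
4. *Section 15.2, question 3.* The truthful answer is *no*.
5. *Section 15.2, question 4.* There are two readings of the branch. If question 4 is not skipped, the problem at question 2 recurs. If it is skipped, the unexposed are kept out, but so are clinicians who see such patients and have chosen never to deprescribe. The *never* category would then be almost empty by construction, since everyone reaching question 4 has said that they have deprescribed.
6. *Section 13.* Nothing removes the person from the percentage for question 2.

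**Illustration**

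Let p be the true *never* share among exposed respondents and f the share of unexposed respondents, all ticking *never*. Neither is in the documents.

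Observed share = p(1 − f) + f; bias = f(1 − p).

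With p = 20%:

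| f | Calculation | Observed | Bias (points) |
|---|---|---|---|
| 2% | 0.98 × 0.20 + 0.02 | 21.6% | 1.6 |
| 5% | 0.95 × 0.20 + 0.05 | 24.0% | 4.0 |
| 10% | 0.90 × 0.20 + 0.10 | 28.0% | 8.0 |
| 20% | 0.80 × 0.20 + 0.20 | 36.0% | 16.0 |

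*Comparison with precision.* The 95% half-width at p = 20% is 1.96 × √(0.20 × 0.80/n). This is 2.8 points at the section 8 target of n = 800 and 7.8 points at n = 100 for one country. The bias exceeds the half-width once f is above half-width/(1 − p): 2.77/0.80 = 3.5% at n = 800, and 7.84/0.80 = 9.8% at n = 100. For p from 10% to 40%, these thresholds run from 2.3% to 5.7% (n = 800) and from 6.5% to 16.0% (n = 100).

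*If some leave a blank.* Suppose half of the unexposed tick *never* and the rest are missing. At p = 20% and f = 5%, the observed share is (0.19 + 0.025)/(0.95 + 0.025) = 0.215/0.975 = 22.1%. If all leave a blank, there is no bias.

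*Comparison of subgroups.* Two professions with the same true 20%, one with f = 2% and the other with f = 20%, would show 21.6% and 36.0%: a gap of 14.4 points with no difference in practice.

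**The case against.** The case on the other side has five parts.

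- *The form does screen.* Question 6 of section 15.1 measures the first alternative directly, and section 10 lists that number among the checked characteristics. Anyone above zero is confirmed eligible, because the alternatives are joined by *or*. This stands. A reader might infer that the form cannot apply section 6 at all; the documents do not support that. The gap is confined to registrants at zero, for whom no rule is stated.
- *Nothing shows that ineligible people enter.* Invitations go to professionals of interest, and the profession item is a closed list of the section 6 groups. This also stands: such entry is possible, not demonstrated. The point does not need it, because an eligible ATT prescriber without end-of-life patients produces the same artefact.
- *The branch after question 3 protects question 4.* It may. The skipped questions are not named, so neither protection nor bias at question 4 can be asserted. Question 2 comes before the branch and is unprotected in either case.
- *The scope is narrow.* This stands. The choice experiment uses hypothetical scenarios, and section 15.4 requires real cases in which deprescribing was considered. Neither turns lack of exposure into *never*.
- *The size is assumed.* Both inputs are, and the main formula takes every unexposed respondent to tick *never*. The direction follows from the scale; the amount does not follow from anything in the documents.

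**Conclusion.** The point holds as a limited defect in one objective 1 item, question 2 of section 15.2, and conditionally in question 4. Section 6 admits respondents who may have no relevant patients, section 10 surveys them, the scale does not let them say so, and section 13 does not set them apart. The *never* percentage can therefore be too high.

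The size is unknown. The move from 20% to 24% rests on an assumed 20% true share, an assumed 5% unexposed, and all of those ticking *never*. What the illustration does show is sensitivity: at 800 respondents and a true 20%, about 3.5% unexposed is enough for the bias to exceed the half-width of the interval.

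A reader might go further and conclude that the descriptive results for objective 1 are biased as a whole, or that a screening question on ATT prescribing would solve the problem. The documents support neither. The artefact belongs to the frequency scale, and a prescriber with no end-of-life patients would pass such a screen and still have only *never* to tick.

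**What to change.** 1. Add *not applicable: I do not see such patients* to questions 2 and 4 of section 15.2.
2. State in section 13 that practice-frequency items are reported among respondents with a number above zero at question 6 of section 15.1, excluding *not applicable* answers. Clinicians who see such patients and never prescribe or never deprescribe stay in the denominator, since theirs is genuine practice. Report the number excluded.
3. Name the questions skipped after a *no* at question 3, and arrange the branch so that genuine *never* answers at question 4 are not lost.
4. Optionally, add a yes/no item on prescribing ATT to cancer patients to section 15.1, so that registrants at zero can be classed against section 6, and state in section 10 what the check does with a zero. This serves eligibility only; without steps 1 and 2 it does not remove the bias.

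The cost is one answer option on two questions and a few sentences in the plan. The filter uses an item already collected. The downside is a slightly smaller denominator for these items.

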7. COUNTRIES INVOLVED

The survey will be conducted among healthcare professionals mainly from the eight European countries represented in the SERENITY consortium:

- Denmark
- France
- Germany
- Italy
- The Netherlands
- Poland
- Spain
- United Kingdom

Due to promotion of the project via international networks and social media (s. section 10), we also expect participants from other countries and regions. Depending on the number or proportion of participants from outside Europe, these will be evaluated separately.

8. (TARGETED) NUMBER OF SUBJECTS

The study aims to generate data from a total of at least 800 healthcare professionals (i.e., either 100 each from the countries listed in section 7 or corresponding participant numbers from additional countries) and up to 2400 anonymised patients, considering that each healthcare professional will be asked to describe actual decisions and anonymous data obtained from medical charts in one to three consecutive patients meeting the definitions below at the time of consideration.

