13. STATISTICAL ANALYSIS

The main analysis of the FMR will be descriptive. Results will be presented for all predefined subgroups and with corresponding 95% confidence intervals. Responses to the DCE will be used to generate preference coefficients for each level of each attribute using random parameters logit regressions, where preference weights represent the relative contribution of the attribute level to the value that participants assigned to an alternative management decision.

The attribute-level coefficients will be expressed as mean preference weights and standard deviations of the mean preference weights, each with appropriate 95% confidence interval. The relative importance of each attribute will be expressed using the within-attribute difference in preference weights as a percentage of the total difference in preference weights across all attributes. For the coefficients, the algebraic sign (positive or negative) of a coefficient reflects whether respondents feel positive or negative with regard to deprescribing. The value of a coefficient indicates the relative importance of the corresponding attribute. The statistical significance of a coefficient ($p \leq 0.05$) indicates that the respondents underline the importance of the attribute within the options in the DCE.

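### Open sign-up with no quota, cap or weighting does not ensure the sample mix of Sections 6 and 8, and non-European respondents can stay in the European figures

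*Combined protocol and SAP*

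**What the plan says.** - **Composition.** Section 6 lists eleven professions and describes the sample as "with equal gender representation and distribution of experienced versus less experienced (young professionals) physicians". It gives no tolerance, no cut between experienced and less experienced, and no level (overall, country or profession) at which balance applies.
- **Numbers.** Section 8: "The study aims to generate data from a total of at least 800 healthcare professionals", made up of "either 100 each from the countries listed in section 7 or corresponding participant numbers from additional countries", and "up to 2400 anonymised patients".
- **Recruitment.** Under Section 10 the national coordinators "will advertise the study through traditional professional networks as well as their social media channels". The section then says "During the preregistration, characteristics of the pre-registrants will be checked" (sex, age, profession, experience, country, yearly patient number), but states no action on the result. After that, "all preregistered participants will be asked simultaneously to complete the survey".
- **Monitoring.** Section 9 follows the number of pre-registrants and adapts recruitment to accrual. It does not mention composition.
- **Respondents from elsewhere.** Section 7 expects them, and makes separate evaluation of those outside Europe depend on their number or proportion, with no threshold. Item 1 in 15.1 lists the eight consortium countries and nothing else.
- **Analysis.** Section 13: "The main analysis of the FMR will be descriptive". It promises 95% confidence intervals for predefined subgroups, which are not listed. Weighting and standardisation are not mentioned.

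**The concern.** The first objective (Section 4) is to describe European practice, and Section 3 expects practice to differ between countries. Section 9 links generalisable conclusions to a large sample. Size reduces sampling error only. If stopping rates differ by country, profession or experience, a pooled proportion takes the value set by whoever signed up, and that part of the error stays the same however many respond. The interval around it does not show this.

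The plan names a target mix but has no stated step to reach it and none to correct for missing it. Because Section 13 is silent on weighting, the choice could also be made after the results are seen. The non-European respondents add a simpler problem: some may be counted in a figure labelled European, and the drafted country item would not show who they are.

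**Working it through.** **1. The plan's own figures.** 8 countries × 100 = 800 professionals, and 800 × 3 = 2400 patients. Both reproduce. The 800 can be met with any country mix, because Section 8 allows substitution from additional countries.

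**2. Nominal precision.** Half-width = 1.96 × √(p(1−p)/n). At p = 0.5:
- n = 800: 3.5 points
- n = 100: 9.8 points
- n = 20: 21.9 points

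The documents give no stopping rates and no sign-up shares. All rates and shares in steps 3 to 6 are assumptions.

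**3. Country mix.** Assume eight country rates evenly spaced from 30% to 60%.
- At 100 each, the pooled rate is 45.0%.
- With sign-up of 20, 20, 40, 60, 80, 130, 200 and 250 (total 800), the crude rate is Σ(n × rate)/800 = 52.5% if the high-rate countries are the large ones, and 37.5% if the order is reversed.
- The shift is 7.5 points either way, against a half-width of about 3.5: 7.5/3.5 = 2.1 times.

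**4. Sex or experience mix.** Shift = (share − 0.5) × difference between groups, in points. The design effect for weighting back to 50:50 is 0.25/share + 0.25/(1 − share).

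| Share | Gap 5 | Gap 10 | Gap 20 | Design effect | Effective n |
|---|---|---|---|---|---|
| 60:40 | 0.5 | 1.0 | 2.0 | 1.04 | 768 |
| 70:30 | 1.0 | 2.0 | 4.0 | 1.19 | 672 |
| 80:20 | 1.5 | 3.0 | 6.0 | 1.56 | 512 |

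Only the 20-point gap with a 70:30 or 80:20 split exceeds 3.5 points.

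**5. Non-European respondents.** Shift = share × difference. If 10% stay pooled, a 10-point difference shifts the figure by 0.10 × 10 = 1 point and a 30-point difference by 0.10 × 30 = 3 points.

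**6. Country results, if shown.** Assume two countries with the same rates within each profession: 60% in palliative care, 30% in cardiology. Country A has a 70/30 mix and country B 30/70.
- A: 0.7 × 60 + 0.3 × 30 = 51%. B: 0.3 × 60 + 0.7 × 30 = 39%. The false gap is 12 points.
- The half-width of a difference at 100 per country is 1.96 × √(0.51 × 0.49/100 + 0.39 × 0.61/100) = 13.7 points.

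The false gap is therefore close to the chance margin but below it. With experience mixes from 60/40 against 40/60 up to 80/20 against 20/80, and group gaps of 10 to 20 points, it runs from 2 to 12 points.

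**7. Price of standardising to equal countries.**
- One country with 400 and seven with 400/7 = 57.1: SE = √((0.25/400 + 7 × 0.25/57.1)/64) = 0.022, half-width 4.3 points.
- The mix in step 3: design effect = 800 × Σ(1/n)/64 = 2.14, effective n about 375, half-width 3.5 × √2.14, about 5 points.
- Many tiny countries, for example 8 with 95 and 8 with 5: SE = √((8 × 0.25/95 + 8 × 0.25/5)/256) = 0.041, half-width about 7.9 points.

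**The case against.** The strongest reply is that the study is exploratory and descriptive, that Section 5 even calls it qualitative, and that the plan has some safeguards. Respondent characteristics are checked before the survey opens, and Section 9 allows recruitment to be adjusted. A reader might infer that the design cannot deliver the stated mix. The documents do not support that: the sponsor could use the check to steer recruitment, and sign-up could turn out balanced. What stands is that no such use is written down, so balance is not assured.

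A reader might also infer that planned country comparisons are invalid. Section 13 names no country contrast, and 100 per country is an aim that Section 8 allows to be substituted. Country results are at most implied by the unlisted subgroups and the rationale in Section 3. Nor does the 12-point example exceed chance variation. The 9.8-point margin belongs to a single country; the margin for a difference is 13.7.

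That the analysis will be unweighted is inferred from silence, not stated.

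Two further objections stand and limit the remedy. An equal-country mean is not a European average, since it ignores country size. With many very small countries it also becomes imprecise (step 7). It should therefore stand beside the crude figure, be confined to the eight listed countries and be protected by a minimum n or trimmed weights.

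**Conclusion.** The point holds in this form: the mix in Section 6 and the country aim in Section 8 are not ensured, no correction is planned, and non-European respondents may remain in the European figures without being identifiable from the drafted country item. Under the assumptions above, the pooled FMR proportion shifts by 7.5 points with very uneven country sign-up, about twice its nominal half-width. Sex or experience imbalance shifts it by 0.5 to 6 points, and in most of those settings the shift is inside the nominal interval. The true distortion cannot be computed from the documents and may be small. The survey and the discrete choice experiment remain usable. What needs support is reading a pooled proportion as European practice, so the change should be made before data are analysed.

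**What to change.** 1. **Sections 7, 13 and 15.1.** Add an other-country option with a specify field to item 1. Always analyse non-European respondents separately and never within the European figures.
2. **Section 13.** Keep the crude pooled proportion. Beside it, report one standardised to the plan's own target: equal weight for the eight listed countries and an equal sex and experience split. Fix in advance a minimum n per country or a trimming rule, the cut across the five experience bands, and the handling of the third sex category. Report the design effect.
3. **Country results, if shown.** List country among the subgroups and also give results standardised for profession group, experience and sex. Professions need grouping: 8 × 11 = 88 cells leave about 800/88 = 9 respondents each. Limit this to the general questions unless the patient-case data, which Section 11 exports and analyses separately, carry coarse respondent groups.
4. **Section 6.** Word balance as an aim, report the achieved composition, and state that self-selection within strata remains after weighting.

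**Cost.** Analysis wording, one extra set of tables and one answer option. The standardised figure has a wider interval: 4.3 points if one country supplies 400 of 800, and about 5 points at a design effect of 2.14, against 3.5 crude.
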